## 9. Study Schedule

FOLLOW UP						
Procedure	Baseline visit	Visit 1	Visit 2	Visit 3	Final visit	Follow-up call
	Day 1	Day 7	Day 30	Day 60	Day 90	Day 105
Eligibility criteria (inclusion and exclusion)	X					
Pregnancy test (if applicable)	X				X	
Informed consent sign	X					
Medical and ophthalmic history (A,B,C).	X	X	X	X	X	
OSDI questionnaire	X	X	X	X	X	
Code assignment to the subject	X					
Visual acuity and Best-corrected visual acuity	X	X	X	X	X	
Conjunctival impression cytology	X				X	
Fluorescein staining	X	X	X	X	X	
Tear break-up time	X	X	X	X	X	
Rose Bengal staining	X	X	X	X	X	
Schirmer Test	X	X	X	X	X	
Anterior biomicroscopy (D, E, F, G, L)	X	X	X	X	X	
Posterior ophthalmoscopy under mydriasis (H, I, J, K)	X				X	
IOP measurement	X				X	
Treatment delivery	X					
Subject journal review	X	X	X	X	X	
Adverse events evaluation		X	X	X	X	
Drug product application	X	X	X	X	X	
Drug product devolution					X	
Concomitant drug product evaluation	X	X	X	X	X	
Safety phone call						X

## 9.1 *Delimitations of the Activities Schedule*

- A. Burning
- B. Foreign body sensation
- C. Tearing
- D. Conjunctival hyperemia
- E. Chemosis
- F. Lens
- G. Iris
- H. Retina
- I. Macula
- J. Vitreous
- K. Excavation of the optic nerve in decimals
- L. Tear film break-up time

## 10. Procedure Description

---

### 10.1 *Medical History*

It refers to a holistic assessment of all factors affecting the subject's health status. Including information about social, cultural, familial, and economic aspects of the subject's life as well as any other component of the life style that affects health and well-being, emphasizing on medical and surgical background, specifying the start, evolution and, according to the case, ending of the previous ailments.

List the medications taken and dates of last dose; specify the route of administration thereof.

A general physical examination, including vital signs (blood pressure, body temperature, breathing per minute and heart rate) and anthropometric parameters (weight, height and complexion) will be performed.

## *10.2 Ophthalmic Clinical History*

Questions about previous ocular chronic or acute ailments will be asked; specifying time of onset or diagnosis and its evolution.

Optical correction devices used by the patient shall be listed if so, such as frame glasses, contact lenses, magnifying, etc. Similarly, evolution time and use period will be expressed.

Subsequently, topical medications used in the eyes and annexes will be investigated, in case there is any systemic medication, it will be written again in this section if it is directly related to an ocular disease or its annexes (eyelids, orbit, lacrimal route, annexed glands, etc.).

## *10.3 Ophthalmic Examination*

### *10.3.1 Visual Acuity Measuring*

Visual acuity will be evaluated basally, without optical correction, with a Snellen chart in a location with adequate natural or artificial lighting, and the result will be recorded on the file in fraction according to the number of lines read by the patient. This data will be reported as visual acuity.

Then the visual acuity of the individual with his best optical refraction will be measured and recorded in the same way it was made on the part of the Snellen chart. This data will be reported as best-corrected visual acuity.

Both data will be reported for statistical purposes in logarithmic figures (LogMAR). A conversion table to LogMAR fraction is attached.

### *10.3.2 Visual Examination Standardization*

- At a distance of 3 m in a proper lighted room the research subject will be evaluated as follows
- This test will be done in the research center .:
- The subject will be asked to sit always in the same place; visual acuity (VA) will be assessed with the scale of LogMAR, if the chart is missing, conversion should be performed (Fig. 10.3.1.1).
- The research subject will keep both eyes open.
- The research subject should gently cover one eye with the occluder provided by Laboratorios Sophia S.A. de C.V., (the same occluder must always be used to cover the eye with all research subjects), while reading aloud the smallest line of letters that he or she can see. This test is done on each eye, one at a time, starting with the right eye (OD).
- The physician should point the line asked to read the research subject.
- The same steps apply for taking best-corrected visual acuity.

LogMAR	VAR	Snellen (m)	Decimal	Snellen (ft)
1.0	50	6/60	0.10	20/200
0.9	55	-	-	20/150
0.8	60	6/36	0.15	20/120
0.7	65	-	0.20	20/100
0.6	70	6/24	-	20/80
0.5	75	6/18	0.30	20/60
0.4	80	-	0.40	20/50
0.3	85	6/12	0.50	20/40
0.2	90	6/9	-	20/30
0.1	95	-	0.75	20/25
0.0	100	6/6	1.00	20/20
-0.1	105	6/5	-	20/15
-0.2	110	6/4	1.50	-
-0.3	115	6/3	2.00	20/10

Fig. No. 10.3.1.1 Table of conversion to LogMAR

### 10.3.3 Biomicroscopy

A sequential order of the eyelids and annexes will be taken to the ocular surface and the anterior chamber. The following points should be gathered:

- ❖ Eyelids, eyelashes and gland annexes description

- ❖ Description of palpebral conjunctiva, bulbar and fornix: at this point we will grade qualitative characteristics as follows.
- ❖ Bulbar hyperemia: It will be related to the images shown in Figure 10.3.3.1 in which different degrees of venous turgor range from very mild, mild, moderate and severe.

[figure not shown]

Fig. 10.3.3.1

- ❖ Tarsal hyperemia: On the same way, the tarsal hyperemia will be related with the images shown in Figure 10.3.3.2, where the venous turgor in the palpebral mucosa is also shown.

Fig. 10.3.3.2

#### 10.3.4 Anterior segment:

- ❖ Fotomotor and consensual pupillary reflexes, as well as the constitution of the iris will be reviewed, highlighting the pathological aspects, as inflammatory membranes, anterior or posterior synechiae, among others.
- ❖ The amplitude of the anterior chamber will be qualitatively graded by amplitude degrees with the Van Herick classification, which gives a degree by subjective assessment of the space between the iris and the posterior surface of the cornea by placing the slit lamp light beam in the outer third of the anterior chamber:

Example: Van Herick II:

- ❖ Lens: points to evaluate are: the integrity of the anterior lens capsule and the characteristics of the composition thereof, highlighting only pathological aspects, e.g. pseudoexfoliation, pigment, synechiae, etc.

[figure not shown]
#### *10.3.5 Fluorescein Staining*

Sodium fluorescein staining will be used on the ocular surface (bulbar conjunctiva and cornea) after the instillation of tetracaine for dilation. Once the surface is stained the following exploration will be performed:

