This epithelial damage includes the death of epithelial cells by apoptosis phenomena, loss of goblet cells and alteration of the expression of the surface mucins, which makes a greater instability on the tear film, a phenomenon that may be started by other etiologies, apart from the hyperosmolarity; i.e. xerofthalmia, ocular allergy, exposure to preservatives or the use of contact lenses. The TDS includes two key physiological factors: Tear film hyperosmolarity and ocular surface inflammation. The lacrimal functional unit (LFU) is responsible of maintaining the integrity of the tear film. The LFU is made by: Main and accessory lacrimal glands, the ocular surface, eye lids and nerves (sensory, motor and autonomic) which interconnect them (reflex arc nervous system). The afferent route is measured by the trigeminal nerve, while the efferent impulses are conducted by the facial nerve. The facial parasympathetic endings regulate the tear composition and keep a proper balance of the aqueous, mucinous and lipid components. Motor endings, on the other hand, are responsible for the hydrodynamic aspects, which will allow a proper lightening, distribution and evaporation of the tear film.

The main causes of the tear hyperosmolarity are the diminishing of the tear aqueous component, associated to the tear gland impairment and/or the increasing on the tear evaporation, favored, overall, by adverse environmental conditions (low environmental humidity, air conditioning, smoke, contamination, autoimmunity pathologies affecting the gland integrity, chronical use of contact lenses, etc.). Increasing of tear evaporation also increases on cases of Meibomian gland dysfunction, which produce an alteration of the lipid component of the tear film. Reduction of the tear aqueous flow has been related with age, reduction of the androgen levels and the effect of some systemic drugs like anticholinergics, anxiolytics, antidepressant, antihistamines, antihypertensive, diuretics, which have been associated with dry eye, as well as with the inflammatory damage over the tear gland that occurs on the Sjogren Syndrome, which destroys the gland tissue.

Changes on the corneal sensibility and a reduction on the tear discharge have been reported on patients who underwent a LASIK surgery.

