### 5.2 *SPECIFIC OBJECTIVES:*

**5.2.1** To evaluate the safety of the preservative-free ophthalmic formulation PRO-087 (by Laboratorios Sophia, S.A. de C.V.) on the corneal and conjunctival epithelium, intraocular pressure, and structures of anterior and posterior segment in patients with tear film dysfunction syndrome from mild to moderate.

**5.2.2** To determine the correlation between improvement of clinical status and perceived improvement of symptoms of each participant in each study group.

**5.2.3** To compare the qualitative and quantitative histological status of the ocular surface before and after the pharmacological intervention in each study group to determine the evolution under the intervention of PRO-087.

**5.2.4** To evaluate the quantitative rating of tear film production by the Schirmer Test throughout the study.

**5.2.5** To qualitatively assess the tear film production by measuring the tear film break-up time stained with fluorescein and cobalt filter.

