#### *10.3.6 Tear Drop Break-up Time*

[figure not shown]
It will be measured at the end of a blink and the patient will be asked not to blink immediately until the tear film on the cornea is broken, if it exceeds 10 " it is considered as normal.

Example:

[figure not shown]

10.3.7 Epithelial Defects on:

10.3.7.1 CORNEA: Epithelial defects will be analyzed by the approximate percentage of the total corneal area, with 100% as all the corneal area. Example:

[figure not shown]

10.3.8 CONJUNCTIVA: It will be qualitatively assessed, according to the extension of the conjunctiva fluorescein deposits, as shown below:

After the fluorescein staining described is done we will take the intraocular pressure (IOP) with a Goldman tonometer, the result will be reported in millimeters of mercury, this is performed only at baseline and final visits.

Once the above aspects are valued, integrate them into a single criterion according to the scale of the University of Oxford, based on this evidence, which proves to have more correlation with the score of the OSDI and Schirmer test.

Panel	Grade	Criterion
A 	0	Equal to or less than panel A

[figure not shown]
[figure not shown]

B		I	Equal to or less than panel B
C		II	Equal to or less than panel C, more than panel B
D		III	Equal to or less than panel D, more than panel C
E		IV	Equal to or less than panel E, more than panel D
> E		V	More than panel E

Fig. 10.3.8.1

10.3.9 Schirmer Test:

Schirmer test involves the quantitative measurement of the amount of tears produced in the eye for 5 minutes, and it is quantified millimetrically on filter paper strips validated for the test. The procedure will be standardized as follows:

1. After instillation of topical tetracaine is instilled over the ocular surface, filter paper strips are placed on the lower lid of the subjects and they will be asked to close their eyes for 5 minutes.
2. After 5 minutes the strips will be removed; the findings will be reported in millimeters.
3. Likewise, assessment will be made as follows:
  - a Normal: > 15 mm
  - b Mild: < 14 mm - > 9 mm
  - c Moderate: > 4 mm. < 80 mm

d      Serious: < 4 mm.

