### 11.1 *Baseline visit:*

1. During the visit, first the informed consent will be checked, clarifying all doubts that the subject wants to review, and recording in the case report format (CRF) the possible questions and the answers given to the subject; this procedure will be carried out strictly by the health staff, preferably by principal investigator.
2. Then, the signing of the informed consent, together with the two witnesses (if applicable) will be done.
3. Eligibility and exclusion criteria will be evaluated.
4. Pregnancy test will be performed (if it applies).
5. The medical staff will provide a patient with a medical history , emphasizing the signs and symptoms related with the systemic inflammatory diseases.
6. A complete ophthalmic clinical history, covering at least the points required on the CRF plus the points required by medical history first used on the research center will be made.
7. An evaluation about all the concomitant drugs will be done.
8. An OSDI questionnaire will be given.
9. A subject number will be given.
10. Ophthalmic examination:
  - a. Visual acuity and best-corrected visual acuity
  - b. Biomicroscopy
  - c. Rose Bengal staining on the ocular surface
  - d. Fluorescein staining on the ocular surface
  - e. Intraocular pressure measuring with Goldman tonometer
  - f. Schirmer Test

- g. Drug induced mydriasis with tropicamide/phenylephrine. Fundoscopy on a slit lamp with a 90D or 78D fundus lens.
- h. Drug product delivery
- i. Impression cytology

11. Delivery of the assigned medication to the subject.

12. Schedule the following visits.

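### Section 10.3.5 puts tetracaine before fluorescein TBUT and Oxford grading, for a purpose that does not fit the plan, and section 11 varies the test order between visits

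*Combined protocol and SAP*

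**What the plan says.** Section 10.3.5 reads "Sodium fluorescein staining will be used on the ocular surface (bulbar conjunctiva and cornea) after the instillation of tetracaine for dilation" and continues "Once the surface is stained the following exploration will be performed". What follows is TBUT (10.3.6), the corneal and conjunctival epithelial defects (10.3.7 and 10.3.8), and an instruction to "integrate them into a single criterion according to the scale of the University of Oxford". On TBUT, section 10.3.6 says "It will be measured at the end of a blink and the patient will be asked not to blink immediately". Objective 5.2.5 confirms that TBUT is read on the stained film: "measuring the tear film break-up time stained with fluorescein and cobalt filter".

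The section 9 schedule marks fluorescein staining, TBUT and Schirmer at days 1, 7, 30, 60 and 90. It marks mydriatic ophthalmoscopy at days 1 and 90 only. For dilation, section 11.1 gives "Drug induced mydriasis with tropicamide/phenylephrine", listed after fluorescein, and the final-visit list does the same. Tetracaine appears elsewhere before the Schirmer strips (10.3.9, citing a paper on Schirmer with and without topical anaesthesia) and before impression cytology (10.4).

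**The concern.** Two things look wrong. First, the reason given for the drop does not match the plan's own use of the drugs, and no other reason is given. Second, an anaesthetic is placed immediately before a measurement of tear film stability. The background in section 3 says that a nervous reflex arc with a sensory limb maintains the film, and it adds: "Changes on the corneal sensibility and a reduction on the tear discharge have been reported on patients who underwent a LASIK surgery". That is enough to ask why TBUT should be timed on an anaesthetised eye. It does not establish what the effect would be.

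The readings carry weight. TBUT above 5 s and below 10 s, and an Oxford grade below III, decide entry (12.1). TBUT below 5 s is an elimination criterion (12.2.3). A rise of 30% or a value of at least 10 s is the TBUT efficacy parameter (14.1.2), and a fall of more than 20% is a safety parameter (14.3.1). The effectiveness rule in 14.1 counts subjects meeting these parameters without reference to a comparator, so a shift common to all arms does not drop out of it.

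**Working it through.** No calculation in the plan bears on this point, so the check sets the sections side by side.

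**Purpose.** Dilating agents named: tropicamide/phenylephrine, at 2 of 5 visits, after fluorescein. Fluorescein staining and TBUT: 5 of 5 visits. Tetracaine in 10.3.9 and 10.4: before Schirmer and cytology, consistent with use as an anaesthetic. Tonometry comes after the fluorescein findings (10.3.8), so it does not explain a drop before them.

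**Order.** The table takes the lists in section 11 as the order of testing.

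| Visit | Schirmer relative to fluorescein (section 11) | Tetracaine instillations before TBUT if 10.3.5 is followed | If the 10.3.5 drop is omitted |
|---|---|---|---|
| Baseline | after | 1 | 0 |
| Day 7 | before (item b; fluorescein f, TBUT g) | 2, or 1 earlier drop if it serves both tests | 1 |
| Day 30 | not listed, though scheduled in section 9 | 1, or more if Schirmer is done first | 0 or 1 |
| Day 60 | before (b; f, g) | 2, or 1 earlier drop if it serves both tests | 1 |
| Day 90 | after | 1 | 0 |

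Either way, days 7 and 60 differ from baseline in number or timing of drops. Baseline and day 90 match as listed.

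**Extent.** 288 subjects × 2 eyes × 5 visits = 2,880 planned readings of TBUT, and as many of staining. The 288 includes the allowance for losses; with the 80 per group of section 13.3 before that allowance, 80 × 3 × 2 × 5 = 2,400. These count readings, not errors.

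**Where a shift would act.** Let b and f be the baseline and follow-up TBUT without tetracaine, and s0 and s1 the unknown additive shifts at the two visits.

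- Entry: b + s0 is compared with 5 and 10 s, so the effective limits become 5 − s0 and 10 − s0.
- Response of +30%: f + s1 ≥ 1.3(b + s0), that is f ≥ 1.3b + 0.3·s0 + (s0 − s1). With equal shifts the bar moves by 0.3·s0; with unequal shifts the full difference s0 − s1 is added.
- Response of at least 10 s: the bar moves by −s1.
- Safety, a fall of more than 20%: f < 0.8b + 0.8·s0 − s1.
- Difference in mean TBUT between arms at one visit: s1 cancels if it is the same in every arm.

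For scale, with b between 5 and 10 s, the 30% rise is 1.5 to 3.0 s and the 20% fall is 1.0 to 2.0 s. The documents give no value or sign for s0 or s1, so no misclassification rate can be computed.

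**The case against.** Several objections are fair.

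- *Dilation* may be a slip, perhaps for dilution of the dye. The text has other apparent slips, such as a Schirmer limit of 100 mm in section 3.1. This is an assumption. It would remove the wrong-purpose point, but tetracaine would still precede the readings.
- Section 11 never places tetracaine beside fluorescein, and its baseline and final lists do not name TBUT. The statement about every visit rests on 10.3.5 and 10.3.6 read with section 9. That reading is sound, but it is an inference.
- One drop before a combined staining and tonometry examination could be a practical choice. The plan does not say so. Section 9 and 10.3.8 confine tonometry to baseline and the final visit, while section 11 lists it at every visit; this also needs reconciling.
- Rose Bengal is listed before fluorescein at all five visits, so removing tetracaine does not leave an undisturbed film.

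A reader might go further and infer that the comparison between lubricants is biased, because section 13.1 plans on a TBUT difference of only 0.15 s. The documents do not support this. That figure is a difference between arms, the procedure is the same in all three, and a common additive shift cancels. It is a poor yardstick in any case: 2 × [(1.96 + 0.84) × 1.1 / 0.15]² = 843.2, or 844 per group (845 with unrounded normal quantiles), against the 32 stated.

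Nor do the documents say that tetracaine adds punctate staining or washes out a lubricant. The remark in section 3 concerns tear discharge after LASIK, not break-up time after a drop. Finally, section 12.2.3 eliminates on TBUT but lists no Oxford grade.

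**Conclusion.** The point holds as a matter of measurement procedure. As written, tetracaine precedes fluorescein TBUT and Oxford grading at all five visits, for a stated purpose that conflicts with the plan's own mydriatics. The listed order also makes tetracaine exposure before TBUT unequal: days 7 and 60 differ from baseline, and day 30 is undetermined. Change from baseline at those visits can therefore mix treatment with procedure, and entry, elimination, response and safety classifications depend on readings whose conditions are not fixed.

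The size is unknown, and so is the direction. The baseline to day 90 comparison is less exposed, because the listed order is the same at both visits. A bias between arms is not demonstrated. The conclusion assumes that sites follow 10.3.5 at each scheduled staining and work through section 11 in the order listed. It merits correction before the first subject, but it does not by itself invalidate the comparison of arms.

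**What to change.** - In 10.3.5, delete the phrase that has tetracaine instilled before fluorescein for dilation. If tetracaine was meant to wet the dye, name what will be used instead.
- State one fixed test order for all visits: fluorescein TBUT and Oxford grading before any tetracaine at that visit; tonometry, Schirmer and cytology afterwards, where scheduled. Give Rose Bengal a fixed place in the same order.
- Reorder the visit lists in sections 11.1 to 11.4 (the final visit is also numbered 11.4) to match. Name TBUT in the baseline and final lists. Reconcile all lists with section 9, including Schirmer at day 30 and the visits at which tonometry is done.

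The cost is small edits to the protocol, the visit lists and site training, with no new procedure. Deleting the phrase alone would not be enough, because days 7 and 60 would still place Schirmer tetracaine before TBUT. The order has to apply from the first subject, so that baseline and follow-up readings are comparable.

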#### *10.3.6 Tear Drop Break-up Time*

[figure not shown]
It will be measured at the end of a blink and the patient will be asked not to blink immediately until the tear film on the cornea is broken, if it exceeds 10 " it is considered as normal.

Example:

[figure not shown]

10.3.7 Epithelial Defects on:

10.3.7.1 CORNEA: Epithelial defects will be analyzed by the approximate percentage of the total corneal area, with 100% as all the corneal area. Example:

[figure not shown]

10.3.8 CONJUNCTIVA: It will be qualitatively assessed, according to the extension of the conjunctiva fluorescein deposits, as shown below:

After the fluorescein staining described is done we will take the intraocular pressure (IOP) with a Goldman tonometer, the result will be reported in millimeters of mercury, this is performed only at baseline and final visits.

Once the above aspects are valued, integrate them into a single criterion according to the scale of the University of Oxford, based on this evidence, which proves to have more correlation with the score of the OSDI and Schirmer test.

Panel	Grade	Criterion
A 	0	Equal to or less than panel A

[figure not shown]
[figure not shown]

B		I	Equal to or less than panel B
C		II	Equal to or less than panel C, more than panel B
D		III	Equal to or less than panel D, more than panel C
E		IV	Equal to or less than panel E, more than panel D
> E		V	More than panel E

Fig. 10.3.8.1

10.3.9 Schirmer Test:

Schirmer test involves the quantitative measurement of the amount of tears produced in the eye for 5 minutes, and it is quantified millimetrically on filter paper strips validated for the test. The procedure will be standardized as follows:

1. After instillation of topical tetracaine is instilled over the ocular surface, filter paper strips are placed on the lower lid of the subjects and they will be asked to close their eyes for 5 minutes.
2. After 5 minutes the strips will be removed; the findings will be reported in millimeters.
3. Likewise, assessment will be made as follows:
  - a Normal: > 15 mm
  - b Mild: < 14 mm - > 9 mm
  - c Moderate: > 4 mm. < 80 mm

d      Serious: < 4 mm.

